TITLE	A randomized, open-label, blinded intravascular ultrasound analysis, parallel group, multicenter study to evaluate the effect of Praluent® (alirocumab) on coronary atheroma volume in Japanese patients hospitalized for acute coronary syndrome with hypercholesterolemia not adequately controlled with statin
INVESTIGATOR/TRIAL LOCATION	JAPAN – Multicenter study
PHASE OF DEVELOPMENT	Phase 4
STUDY OBJECTIVE(S)	Primary objective: To compare the effect of Praluent® with standard of care (SoC) on coronary atheroma progression (percent change in normalized total atheroma volume [TAV]) after 9 months of treatment in patients who had acute coronary syndrome (ACS) within 4 weeks prior to randomization, with hypercholesterolemia treated with any statin Secondary objective(s): 
• To compare the effect of Praluent® with SoC on secondary endpoints including absolute change in percent atheroma volume (PAV) and normalized TAV after 9 months of treatment• To evaluate the effect of Praluent® on low-density lipoprotein cholesterol (LDL-C), apolipoprotein B (Apo B), triglycerides, non-high-density lipoprotein cholesterol (non-HDL-C) and Lipoprotein(a)(Lp(a)) after 9 months treatment• To evaluate the safety of Praluent® including the occurrence of cardiovascular (CV) events (coronary heart disease [CHD] death, non-fatal myocardial infarction [MI], fatal and non-fatal ischemic stroke, unstable angina requiring hospitalization) throughout the study
STUDY DESIGN	Open-label, 1:1 randomized, blinded intravascular ultrasound (IVUS) analysis, 2-arm, parallel-group, multicenter study Randomization will be stratified by on statin therapy or not on statin therapy at the time of ACS onset. After randomization, patients will receive open-label study treatment of Praluent® 75 mg every 2 weeks (Q2W) on top of stable daily statin therapy for 36 weeks, or SoC. For patients randomized to alirocumab arm, a dose up-titration to Praluent® 150 mg Q2W may be conducted at Week 14 based on LDL-C level at Week 12 (see below). For patients randomized to SoC arm, LDL-C target level <100 mg/dL is achieved with stable dose statin therapy (within the range of statin doses approved by the Health Authority) ± other lipid modifying therapies (LMTs) except for anti-PCSK9 monoclonal antibody. Concomitant non-statin LMTs will be considered if LDL-C target level <100 mg/dL cannot be achieved with statin monotherapy. LDL-C is managed to achieve target level <100 mg/dL using the

	
above mentioned or other method.
 
The study consists of:
 
• A 36-week open label treatment period (study period)• During the study period, patients randomized to alirocumab or SoC arm will receive treatment in an un-blinded manner as follows. 
1. Alirocumab arm:
 
• Praluent® (alirocumab) 75 mg Q2W subcutaneously on top of statin therapy (atorvastatin \geq10 mg/day or rosuvastatin \geq5 mg/day) within the range of statin doses approved by the Health Authority.• Statin (atorvastatin \geq10 mg/day or rosuvastatin \geq5 mg/day within the range of statin doses approved by the Health Authority) and non-statin LMTs will be continued at the same doses after ACS diagnosis unless modifications are necessary. The target LDL-C level is $<$100 mg/dL.• At Week 14, patients randomized to alirocumab arm will, in an un-blinded manner, either:
- Continue receiving Praluent® (alirocumab) 75 mg Q2W if the Week 12 LDL-C measured by the central laboratory is $<$100 mg/dL OR- Receive dose up-titrated to Praluent® (alirocumab) 150 mg Q2W at Week 14, if the Week 12 LDL-C measured by the central laboratory is \geq100 mg/dL. 
Continuation of Praluent® 75 mg Q2W or dose up-titration to Praluent® 150 mg Q2W will occur at each study site based on the rules as above.
 
• Self-injection of Praluent® (alirocumab) at home
- Patients can choose self-injection at home any time, if they wish self-injection at home and the Investigator or sub-Investigator considers it feasible.- Patients are allowed to perform self-injection at home if they successfully perform the correct self-injection of Praluent® (alirocumab) under the direct supervision of site medical staff at the site once, and the Investigator or sub-Investigator considers that they can perform self-injection at home correctly.- Regardless of the timing when the self-injection is started, patients must visit the study site at least every 4 weeks, and at Week 0, Week 4, Week 12, Week 14, Week 24 and Week 36.- Patients can discontinue self-injection at home any time. The Investigator or sub-Investigator must have patients discontinue self-injection at home if the Investigator or sub-Investigator judges that the patients are not able to perform self-injection at home correctly. Patients who discontinue self-injection at home can have injections performed by medical staff at the study site.
--	---

	
2. Standard of Care arm:
 
During the study period, patients randomized to the SoC arm will, in an un-blinded manner, receive either:
Stable dose statin therapy of either atorvastatin ≥ 10 mg/day or rosuvastatin ≥ 5 mg/day (within the range of statin doses approved by the Health Authority) to achieve the LDL-C target level <100 mg/dL.Concomitant non-statin LMTs if LDL-C target level <100 mg/dL cannot be achieved with statin monotherapy. Adjustment of LMTs is to be performed based on, but not limited to, the above rule.

STUDY POPULATION
 
Main selection criteria
	
Main inclusion criteria:
 
I 01. Patients hospitalized for ACS (ST-elevation myocardial infarction [STEMI], non ST-elevation myocardial infarction [NSTEMI], unstable angina).
 
I 02. LDL-C ≥ 100 mg/dL at ACS diagnosis (either by Friedewald method or direct method measured at each study site).:
a) Patients who have already been on any statin therapy at ACS onset. If the statin is not atorvastatin or rosuvastatin, statin will be changed to either atorvastatin ≥ 10 mg/day or rosuvastatin ≥ 5 mg/day immediately after the ACS diagnosis based on Investigators' medical judgment.b) If patients have not been on any statin therapy at ACS onset, either atorvastatin 10 mg/day or rosuvastatin 5 mg/day is started immediately after the ACS diagnosis, and LDL-C is not adequately controlled with statin at 2 to 4 weeks after the ACS diagnosis (in principle, LDL-C target level ≥ 100 mg/dL, but this may not apply if the responsible physician considers the LDL-C level inadequate on statin. Patients who have LDL-C <70 mg/dL cannot be enrolled).
 
I 03. Patients who has stenosis of at least 50% on coronary angiography within 1 week after the ACS onset, and has analyzable coronary IVUS image. The evaluated segment of IVUS is a segment where a physician considers the IVUS imaging is possible (regardless of culprit vessels or not culprit vessels) other than the culprit lesions.
 
I 04. Patients aged ≥ 20 years old at ACS diagnosis.
 
I 05. Patients who meet any of the following conditions:
- Negative hepatitis B virus surface antigen, negative hepatitis B virus total core antibody, and negative hepatitis C virus antibody.- Negative hepatitis B virus surface antigen, positive hepatitis B virus total core antibody, negative hepatitis B virus DNA, and negative hepatitis C virus antibody.
 
I 06. Written informed consent.

	
Main exclusion criteria:
 
E 01. Patients who have been previously treated with at least one dose of any anti-PCSK9 monoclonal antibody.
 
E 02. Uncontrolled hypertension (multiple reading with systolic blood pressure [SBP] > 180 mmHg or diastolic blood pressure [DBP] >110 mmHg) between ACS diagnosis and randomization visit.
 
E 03. Known history of hemorrhagic stroke.
 
E 04. Currently under treatment with anticancer drug.
 
E 05. Patients on LDL apheresis.
 
E 06. Conditions/situations such as:
 
• Any clinically significant abnormality identified that in the judgment of the Investigator or any sub-Investigator would preclude safe completion of the study or constrain endpoints assessment such as major systemic diseases, patients with short life expectancy.• Considered by the Investigator or any sub-Investigator as inappropriate for this study for any reason, e.g.:
- Those deemed unable to meet specific protocol requirements, such as scheduled visits.- Investigator or any sub-Investigator, pharmacist, study coordinator, other study staff or relative thereof directly involved in the conduct of the protocol, etc.- Presence of any other condition (e.g., geographic, social, etc.) actual or anticipated, that the Investigator or sub-Investigator feels would restrict or limit the patient's participation for the duration of the study. 
E 07. Laboratory findings measured before the randomization visit within 4 weeks after the ACS diagnosis.
 
• Positive serum or urine pregnancy test in women of childbearing potential.
Total expected number of patients	200
STUDY TREATMENT(s)	SoC (stable dose statin therapy \pm other LMTs targeting LDL-C <100 mg/dL) and combination therapy (stable dose statin therapy + Praluent® 75 mg Q2W subcutaneously with up-titration to 150 mg Q2W at Week 14 if LDL-C <100 mg/dL is not achieved.)
Investigational medicinal product(s)	Praluent® (Alirocumab)
Formulation:	Alirocumab, an active ingredient of Praluent®, is a fully human monoclonal antibody that binds PCSK9.
Route(s) of administration:	Praluent® will be supplied in a 1 mL autoinjector as an injectable drug with pH 6.0, containing histidine, polysorbate 20, and sucrose, with alirocumab concentration of 75 mg/mL or 150 mg/mL.
Dose regimen:	Subcutaneous administration to the abdomen, thighs, or outer area of the upper arms
	Dose regimen approved in Japan: 75 mg Q2W with up-titration to 150 mg Q2W if LDL-C <100 mg/dL is not achieved.

[figure not shown]
Noninvestigational medicinal product(s)	
• Atorvastatin• Rosuvastatin• Cholesterol absorption inhibitor (ezetimibe)• Fibrates (fenofibrate, bezafibrate)• Anti-platelets (aspirin, clopidogrel, etc.)• Warfarin, and other oral anticoagulants approved in Japan
Route(s) of administration:	Oral
Dose regimen:	Dose regimen approved in Japan
ENDPOINT(S)	
Primary efficacy endpoint:
 
• Percent change in normalized TAV from baseline to Week 36 
Key secondary efficacy endpoint:
 
• Absolute change in PAV from baseline to Week 36 
Other secondary efficacy endpoint(s):
 
• Absolute change in normalized TAV from baseline to Week 36• Absolute and percent change in external elastic membrane (EEM) volume from baseline to Week 36• Absolute and percent change in lumen volume from baseline to Week 36• Absolute and percent change in calculated LDL-C from baseline to Week 12, and Week 36• Absolute and percent change in Apo B from baseline to Week 36• Absolute and percent change in non-HDL-C from baseline to Week 36• Absolute and percent change in total cholesterol (TC) from baseline to Week 36• Absolute and percent change in Lp(a) from baseline to Week 36• Absolute and percent change in HDL-C from baseline to Week 36• Absolute and percent change in fasting triglycerides (TGs) from baseline to Week 36• Absolute and percent change in apolipoprotein A-1 (Apo A-1) from baseline to Week 36 
Safety endpoints:
 
• Safety parameters (adverse events including CV events*, laboratory data and vital signs) assessed throughout the study

	
*CV events: CHD death, non-fatal MI, fatal and non-fatal ischemic and/or haemorrhagic stroke, unstable angina requiring hospitalization, congestive heart failure requiring hospitalization, ischemia-driven coronary revascularization.

ASSESSMENT SCHEDULE	
Patient's assessments in the treatment period: On-site visits: Week 0 (randomization visit), Week 4, Week 12, Week 24, Week 36

STATISTICAL CONSIDERATIONS	
Sample size determination: The study is expected to enroll approximately 200 patients. Based on the results of ZEUS(1) and PRECISE-IVUS(2) studies, it is assumed that difference in percent change in normalized TAV from baseline between alirocumab arm and SoC arm is 8%, and the common standard deviation of percent change in normalized TAV is 15%. Under the assumption, a sample size of 150 patients (75 in the alirocumab arm and 75 in the SoC arm) will have 90% power to detect the treatment difference with two-sided significance level of 5%. Assuming that proportion of non-evaluable primary endpoint is 25%, it is considered that 200 patients (100 in the alirocumab arm and 100 in the SoC arm) will be needed.
 
Analysis population: Randomized population includes all patients who have been allocated to a randomized treatment and recorded in the registration center database, regardless of whether a study drug was used or not. The primary efficacy analysis population will be the modified intent-to-treat (mITT) population, defined as the randomized population who takes at least one dose or part of dose of study drug and has an available value of normalized TAV before randomization and after 24 weeks of treatment. Patients in the mITT population will be analyzed according to the treatment arm allocated by randomization. The safety population consists of patients of randomized population who actually received at least one dose or partial dose of study treatment. The safety population will be analyzed according to the treatment actually received.
 
Primary analysis: The percent change in normalized TAV will be analyzed using an analysis of covariance (ANCOVA) model with treatment arm and randomization strata as fixed effects, and the baseline normalized TAV as covariate.
 
Analysis of Key secondary efficacy endpoints: Analysis of key secondary efficacy endpoint will be performed on the mITT population considering corresponding baseline value as covariate, in the same manner as for the primary endpoint.
 
Multiplicity adjustment: A hierarchical procedure will be used to control the type I error and to handle multiple endpoints. If the primary endpoint analysis is significant at the two-sided 5% alpha level, the key secondary

	
efficacy endpoint will be tested at the two-sided 5% level. The other secondary efficacy endpoints not included in key secondary endpoint will be analyzed for exploratory purpose only.
 
Safety analysis:
 
Safety analysis will be descriptive, based on the safety population. Safety analysis will focus on the Treatment Emergent Adverse Events (TEAE) period defined as the time from the day of randomization to the last administration + 21 days (3 weeks), or end of study, whichever comes first.
 
The treatment arm allocation for as-treated analysis will be defined as follows:
 
• Alirocumab arm if proportion of IMP injection is $\geq 50\%$.• SoC arm if proportion of IMP injection is $< 50\%$. 
where proportion of IMP injection (%) is defined as:
 $100 \times (\text{Number of IMP injection}) / [(\text{Date of end of treatment} - \text{Date of randomization}) / 14 + 1]$
DURATION OF STUDY PERIOD (per patient)	9 months

1 FLOW CHARTS

1.1 GRAPHICAL STUDY DESIGN

Abbreviations: ACS, acute coronary syndrome; IC, informed consent; IVUS, intravascular ultrasound; LDL-C, low-density lipoprotein cholesterol; LMT, lipid modifying therapy; Q2W, every 2 weeks; R, randomization; SoC, standard of care.

- a If patients have not been on any statin therapy at ACS onset, either atorvastatin 10 mg/day or rosuvastatin 5 mg/day is started immediately after the ACS diagnosis.
- b At randomization, patients should have already received stable statin therapy with either atorvastatin ≥10 mg/day or rosuvastatin ≥5 mg/day for at least 2 weeks.
- c Stable dose statin monotherapy (atorvastatin ≥10 mg/day or rosuvastatin ≥5 mg/day within the range of statin doses approved by the Health Authority) will be administered to achieve the LDL-C target level <100 mg/dL. Concomitant non-statin LMTs will be considered if patients have already been on them on top of statin monotherapy at the time of ACS diagnosis or if LDL-C target level <100 mg/dL cannot be achieved by the statin monotherapy. Adjusting of LMT will occur based on above rule, but not limited.
- d Praluent® 75 mg Q2W on top of stable dose of atorvastatin ≥10 mg/day or rosuvastatin ≥5 mg/day ± other LMTs, in accordance with doses approved by the Health Authority. Concomitant non-statin LMTs will be considered if patients have already been on them on top of statin monotherapy at the time of ACS diagnosis. Background statin and/or non-statin LMT regimens should not be changed as a principle during the entire study period.
- e In the alirocumab arm, if LDL-C level at Week 12 measured by the central laboratory does not reach <100 mg/dL, Praluent® dose up-titration to 150 mg Q2W will be carried out at Week 14.
- f Patients who perform self-injection of Praluent® at home must visit the study site at least every 4 weeks, and at Week 0, Week 4, Week 12, Week 14, Week 24 and Week 36.

1.2 STUDY FLOW CHART

	Treatment																	EOT	
	W0	W2	W4	W6	W8	W10	W12	W14	W16	W18	W20	W22	W24	W26	W28	W30	W32	W34	
Week (W)	W0	W2	W4	W6	W8	W10	W12	W14	W16	W18	W20	W22	W24	W26	W28	W30	W32	W34	W36
Day (D)	D1	D15	D29	D43	D57	D71	D85	D99	D113	D127	D141	D155	D169	D183	D197	D211	D225	D239	D253
Visit Number	1 ^a		2				3						4						5
Visit Window (D)			±7				±7						±7						±14
Design																			
Informed consent	X ^b																		
On-site visit	X		X				X						X					X	
Inclusion criteria/ Exclusion criteria	X																		
Patient demography	X																		
Medical / family / surgical history, alcohol habits, smoking habits	X ^c																		
Prior medication history	X																		
Physical examination	X																		
Body weight	X						X						X					X	
Height	X																		
Randomization	X																		
Registration center contact	X																	X	
Treatment																			
Praluent® administration ^m	X	X	X	X	X	X	X	X	X	X	X	X	X	X	X	X	X	(X) ^d	
Praluent® administration window (D)		±7	±7	±7	±7	±7	±7	±7	±7	±7	±7	±7	±7	±7	±7	±7	±7		
Phone-call interview ^e					X				X		X			X		X			
Compliance check (IMP/NIMP) ^e	X		X		X		X		X		X		X		X		X		
Vital signs																			
Heart rate	X		X				X						X					X	
Blood pressure (sitting position)	X		X				X						X					X	
Efficacy																			
IVUS imaging	X ^f																	X ^g	
Transfer IVUS imaging data to central reading laboratory	X																	X	

	Treatment																	EOT	
	W0	W2	W4	W6	W8	W10	W12	W14	W16	W18	W20	W22	W24	W26	W28	W30	W32	W34	
Week (W)	W0	W2	W4	W6	W8	W10	W12	W14	W16	W18	W20	W22	W24	W26	W28	W30	W32	W34	W36
Day (D)	D1	D15	D29	D43	D57	D71	D85	D99	D113	D127	D141	D155	D169	D183	D197	D211	D225	D239	D253
Visit Number	1 ^a		2				3						4					5	
Visit Window (D)			±7				±7						±7					±14	
Safety																			
AE/SAE recording including CV events	X		X		X		X		X		X		X		X		X	X	
Laboratory testing - Efficacy																			
TC, calculated LDL-C, HDL-C, TG, non-HDL-C	X ^b		X				X						X					X	
Apo B, Apo A-1, Apo B/Apo A-1 ratio, Lp(a)	X																	X	
Laboratory testing - Safetyⁱ																			
Hematology and chemistry ^j	X		X				X						X					X	
Hepatitis B virus core antibody ⁿ	X																		
Hepatitis C virus antibody	X																	X	
Serum pregnancy test ^k	X																		
Urine pregnancy test ^k	X																	X	
Laboratory testing - Others																			
HbA1c	X						X						X					X	
hs-CRP	X																	X	
Quality of Life Variables																			
EQ-5D patient questionnaire ^l	X		X				X						X					X	

Abbreviations: AE, adverse event; Apo A-1, apolipoprotein A-1, Apo B, apolipoprotein B; CV, cardiovascular; D, day(s); EOT, end of treatment; HbA1c, hemoglobin A1c; HDL-C, high-density lipoprotein cholesterol; hs-CRP, high sensitivity C-reactive protein; IMP, investigational medicinal product; IVUS, intravascular ultrasound; LDL-C, low-density lipoprotein cholesterol; NIMP, noninvestigational medicinal product; non-HDL-C, non-high-density lipoprotein cholesterol; SAE, serious adverse event; TC, total cholesterol; TG, triglyceride; W, week.

a Randomization visit (Visit 1) is conducted after the assessment of candidate patients for inclusion/exclusion criteria.

b Informed consent is obtained between ACS diagnosis and Visit 1.

c Patient medical history includes lipid parameters (i.e., LDL-C used for patient selection) used for the study eligibility and HbA1c.

d Praluent® is administered at Week 36 if the patient cannot complete the evaluation IVUS by Week 36. It should be noted that the final lipid values will be recorded at Week 36 (V5) as EOT.

e Phone call interview will be carried out only for the patients assigned to the SoC arm. Review of IMP / NIMP administration status includes the compliance with diet therapy recommended by the Japan Atherosclerosis Society Guideline or equivalent.

f Baseline IVUS study will be performed as following standard protocol in each site. Baseline IVUS imaging data will be transferred to the central reading laboratory.

g Evaluation IVUS is carried out on V5 / Week 36 ± 14 days (between Week 34 and Week 38). The IVUS imaging data will be transferred immediately after the evaluation IVUS is obtained.

h Lipid parameters will be measured at the study sites and will be used for the patient selection before randomization. The lipid parameters will be also recorded as part of the patient demography.

- i* Laboratory testing data for safety assessment except hepatitis B virus core antibody and hepatitis C virus antibody will be collected from each study site.
- j* Hematology laboratory testing includes red blood cell count, hematocrit, hemoglobin, white blood cell count with differential count, and platelet count. Chemistry laboratory testing includes glucose, sodium, potassium, chloride, creatinine, uric acid, lactate dehydrogenase (LDH), total protein, albumin, gamma-glutamyl transpeptidase (γ GT), creatine phosphokinase (CPK), alanine aminotransferase (ALT), aspartate aminotransferase (AST), alkaline phosphatase (ALP), and total bilirubin.
- k* Women of childbearing potential (WOCBP) only.
- l* EQ-5D patient questionnaire interview will be carried out for all patients on study treatment. For prematurely (permanently) discontinued patients, the last questionnaire interview will be carried out at the EOT visit defined in the protocol (see [Section 10.3](#)).
- m* Patients can choose self-injection of Praluent® at home any time, if they wish self-injection at home and the Investigator/sub-Investigator considers it feasible.
Before starting self-injection at home, the Investigator/sub-Investigator must explain to the patients using the operation procedure for administration of IMP. If necessary, patients can use the training kits. Patients are allowed to perform self-injection at home if they successfully perform the correct self-injection of Praluent® under the direct supervision of site medical staff at the study site once, and the Investigator/sub-Investigator considers that they can perform self-injection at home correctly. They can use tools to assist.
Regardless of the timing when the self-injection is started, patients must visit the study site at least every 4 weeks, and at Week 0, Week 4, Week 12, Week 14, Week 24 and Week 36.
Patients must record self-injection at home in the diary. At each visit, they must bring the diary, and the site medical staff must check their records. If self-injection at home is performed, IMPs will be provided for only number of times of self-injections at home until the next visit. Patients must return used and unused IMPs to the site medical staff at the next visit.
Patients can discontinue self-injection at home any time. The Investigator/sub-Investigator must have patients discontinue self-injection at home, if the Investigator/sub-Investigator judges that the patients are not able to perform self-injection at home correctly. Patients who discontinue self-injection at home can have injections performed by medical staff at the study site.
- n* Hepatitis B virus DNA will be measured promptly if hepatitis B virus total core antibody comes back positive.

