It is recommended that blood pressure is measured in the sitting position under the same conditions each time, approximately at the same time of the day, on the same arm, with the same

apparatus (after the patient has rested in sitting position for at least 5 minutes). Both systolic and diastolic blood pressure should be recorded. It should be noted that blood pressure should be measured in both arms at the randomization visit (Week 0). The arm with the highest diastolic blood pressure will be used to measure the blood pressure throughout the study. The highest blood pressure value will be recorded in the e-CRF.

The heart rate will also be measured at the time of blood pressure measurement.

Note: In cases with hypertension (high blood pressure values) (within 4 weeks prior to the randomization or after ACS onset and prior to the randomization) the Investigator/sub-Investigators is responsible for the optimization of the patient's treatment to achieve blood pressure target as defined by local guidelines (Japanese Society of Hypertension) or the Seventh Report of the Joint National Committee on Prevention, Detection, Evaluation, and Treatment of High Blood Pressure (JNC7).

Body weight and height:

Body weight should be obtained with the patient wearing undergarments or very light clothing and no shoes, and with an empty bladder. The same scale should be used throughout the study. The use of calibrated balance scales is mandatory. Self-reported weights are not accepted. Patients must not read the scale themselves. Height should be measured and self-reported heights are not accepted.

EQ-5D patient questionnaire:

Collection of EQ-5D patient questionnaire will be carried out in all patients at each scheduled visit (5 visits) by Investigator, or a person designated by the Investigator.

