10.2 DEFINITION OF SOURCE DATA

Evaluations that are reported in the e-CRF must be supported by appropriately signed identified source documentation related but not limited to the following:

- Agreement, date, and signature of informed consent mentioning the study identification.
- Patient identification, last participation in a clinical trial, medical history, associated disease, and data related to the studied pathology.
- Contraception methods for women of childbearing potential.
- Previous and concomitant medication (including the LMT).
- Study identification.
- Treatment number, dates of administration.
- Dates of visit and assessments including the examination report.
- Vital signs, height, body weight.
- Central laboratory reports (dated and signed by the Investigator or sub-Investigator).
- Laboratory values at study site (dated and signed by the Investigator or sub-Investigator)
- The registration center confirmation reports (randomization, discontinuation, and the end of the study).
- ECG records with physician's signature and dated.
- AEs and follow-up:
 - In case of SAE, the study site should file as the source document at least copies of the hospitalization reports and any relevant examination reports documenting the follow up of the SAE.
- Date of premature study discontinuation (if any) and reasons.

Source documentation may be found in the followings:

- Patient's identity.
- Medical history.
- Hospital records.
- Nursing notes.

- Physician's notes.
- Laboratory reports.

10.3 HANDLING OF PATIENT TEMPORARY OR PERAMENANT TREATMENT DISCONTINUATION AND OF PATIENT STUDY DISCONTINUATION

Study treatment should be continued whenever possible. In case the treatment is discontinued, it should be determined whether the discontinuation can be made temporarily; permanent treatment discontinuation should be a last resort. Any treatment discontinuation should be fully documented in the Case Report Form (CRF). In any case, the patient should remain in the study as long as possible.

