10.3.4 Handling of patients after permanent treatment discontinuation (SoC or IMP)

- All definitive discontinuation of study treatment should be recorded by the Investigator in the appropriate screens of the e-CRF and in the patient's medical records when considered as confirmed. The registration center should be notified when a patient prematurely discontinues the study. Patients should be asked to stick to the visit schedule for measuring laboratory test values until the end of study (Week 36).
- When patients permanently discontinue the study (regardless of the reasons) before Week 24 (6 months), they will have an unscheduled on-site visit as soon as possible (preferably within 7 days from treatment discontinuation) with assessments originally planned at the EOT visit (Week 36).
- When patients in the alirocumab arm permanently discontinue the study (regardless of the reasons) on Week 24 (6 months) or after, the Investigator should make the best effort to schedule the evaluation IVUS imaging with assessments originally planned at the EOT visit (Week 36) within 2 weeks from the last IMP administration (the earliest last IMP administration occurs on Week 22). If the patients decline the evaluation IVUS imaging after the study discontinuation, they will have an unscheduled on-site visit as soon as possible (preferably within 7 days from treatment discontinuation) with assessments originally planned at the EOT visit (Week 36).
- When patients in the SoC arm permanently discontinue the study (regardless of the reasons) on Week 24 (6 months) or after, the Investigator should make the best effort to

schedule the evaluation IVUS imaging with assessments originally planned at the EOT visit (Week 36) within 2 weeks from the determination date of the study discontinuation. If the patients decline the evaluation IVUS imaging after the study discontinuation, they will have an unscheduled on-site visit as soon as possible (preferably within 7 days from treatment discontinuation) with assessments originally planned at the EOT visit (Week 36).

- When patients, who develop AEs including AESIs and/or SAEs and need to be followed up as specified in this protocol, permanently discontinue the study, they will be followed up until recovery or stabilization of the AEs.

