### **2.3.3 Quality-of-life population**

The analyses of QOL will be performed on all randomized and treated patients (safety population) with a baseline and at least 1 matching post-baseline evaluation for any of the 5 dimensions. Patients will be analyzed according to the treatment actually received.

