### ***EQ-5D utility score***

The raw value and the absolute change from baseline of the utility score will be summarized using mean, median, Q1, Q3, SD, minimum, and maximum for each post-baseline visit. Cumulative distribution functions for the absolute change in utility score from baseline will be displayed by treatment groups, at Week 4, Week 12, Week 24, and Week 36.

The absolute change from baseline in utility score to Week 4, Week 12, Week 24, and Week 36 will be analyzed using a MMRM model with fixed categorical effects of treatment group, randomization strata as per the registration center, treatment-by-time point interaction, strata-by-time point interaction, as well as, the continuous fixed covariates of baseline value and baseline value-by-time point interaction.

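### Flow chart footnote l and Section 10 disagree on whether EQ-5D continues after a patient stops study treatment, so later values needed by the quality-of-life model may not be collected

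*Protocol*

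**What the plan says.** The protocol gives two collection rules for EQ-5D.

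- **Section 1.2, footnote l:** "EQ-5D patient questionnaire interview will be carried out for all patients on study treatment". The footnote continues: "For prematurely (permanently) discontinued patients, the last questionnaire interview will be carried out at the EOT visit defined in the protocol", and refers the reader to Section 10.3.
- **Section 10, EQ-5D paragraph:** "Collection of EQ-5D patient questionnaire will be carried out in all patients at each scheduled visit (5 visits", that is, Weeks 0, 4, 12, 24 and 36. The lists for Visits 1 to 5 in Section 10.1.1.1 each include EQ-5D, with no condition that the patient still be on treatment.

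Two further passages bear on patients who stop.

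- **Opening of Section 10.3:** "In any case, the patient should remain in the study as long as possible".
- **Section 10.3.4:** "Patients should be asked to stick to the visit schedule for measuring laboratory test values until the end of study (Week 36"; EQ-5D is not named. For patients who discontinue the study before Week 24, "they will have an unscheduled on-site visit as soon as possible (preferably within 7 days from treatment discontinuation", with the assessments planned for the EOT visit. EQ-5D is one of these.

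On analysis, SAP Section 2.3.3 defines the quality-of-life population as treated patients who have a baseline and one or more later EQ-5D evaluations, grouped by the treatment they in fact received. SAP Section 2.4.7 says: "The absolute change from baseline in utility score to Week 4, Week 12, Week 24, and Week 36 will be analyzed using a MMRM model". Its terms include treatment group and treatment-by-time point, and values are assigned to time points by the Table 4 windows. SAP Section 2.5.5 lets an unscheduled value serve a time point if it fits that definition.

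**The concern.** A patient who stops treatment but keeps attending Weeks 12, 24 and 36 is covered by two rules that give different answers. Section 10 and the visit lists say the questionnaire is given; footnote l says it ends with the EOT interview. Section 10.3.4 does not resolve this, because it names only laboratory tests.

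If a site follows footnote l, the later EQ-5D values are absent because treatment stopped. Among the reasons for stopping in Section 10.3.3 are adverse reactions and harm to the patient's well-being, so a link with health status is plausible. The MMRM then relies on the later values being predictable from the earlier ones, arm and stratum. The SAP's missing-data sensitivity analyses cover only the primary endpoint (Section 2.4.4.1) and the key secondary endpoint (Section 2.4.4.2). Sites may also apply different rules, and values not collected cannot be recovered afterwards.

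**Working it through.** The plan states no figure for EQ-5D, so there is nothing to reproduce. The check has two parts.

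**1. What each rule collects after a stop.** Take a patient who stops on Day 50 and remains in the study.

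- Section 10: EQ-5D at Weeks 12, 24 and 36.
- Footnote l, with the EOT interview held early (say 7 days later, Day 57): one value, on Day 57, and none at the scheduled visits.
- Footnote l, with the EOT visit read as Visit 5: one value at Week 36; Weeks 12 and 24 missing.

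The last two readings are both open. Footnote l speaks of permanently discontinued patients, whereas the early-visit bullets in 10.3.4 are worded for patients who discontinue the study.

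**2. Whether an early EOT value reaches the model.** SAP Table 4 windows, in study days:

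- Week 4: 15 to 42
- Week 12: 78 to 98
- Week 24: 155 to 182
- Week 36: 239 to 266

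The early visit applies before Week 24 (Day 169). From the first windowed day to the day before Week 24:

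- Days 15 to 168 = 168 − 15 + 1 = 154 days.
- In a window: 28 (Days 15–42) + 21 (Days 78–98) + 14 (Days 155–168) = 63.
- In a gap: 35 (Days 43–77) + 56 (Days 99–154) = 91.
- Share in a gap: 91 / 154 = 59%.

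Two variants give similar shares:

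- Visit on any day from Day 2 to Day 168: 63 of 167 days are in a window, so 104 / 167 = 62% are not.
- Stop on any day from Day 2 to Day 168 with the visit 7 days later: 70 of 167 stop days give a usable value, so 97 / 167 = 58% do not.

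These are shares of days. They become probabilities only if stops are spread evenly over the period, which is an assumption.

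In the Day 50 example the Day 57 value falls in the 43–77 gap. The patient contributes Week 4 to the MMRM and nothing at Weeks 12, 24 or 36. Section 10 would have supplied all three.

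**The case against.** The strongest reply is that the body of the protocol already supports continued collection. Section 10 says all patients at five visits, every visit list includes EQ-5D without condition, and Section 10.3 wants patients kept in the study. Footnote l itself requires a final interview, which can be read as the Week 36 visit. So the documents are ambiguous; they do not prescribe a loss. This stands, and it is why the point is a conflict to be reconciled.

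A reader might infer more than the documents support:

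- **That EQ-5D ends the moment treatment ends.** The second sentence of footnote l provides for an EOT interview.
- **That patients who stop drop out of the model.** The MMRM keeps every in-window value before the stop. Only later time points are lost, except for a patient who stops before giving any in-window value.
- **That the contrast is biased towards alirocumab.** The loss may be unequal: Section 10.3.3 sets the adherence criterion at 12 weeks for alirocumab and 6 months for SoC, and lists injection-site reactions among the reasons to stop. But discontinuation is defined for SoC too. The only stopping rates in the documents, for adverse events in the Japanese phase 3 study (Section 4), are 4.9% on alirocumab and 5.6% on placebo. Suppose, purely as an assumption, that stoppers score 0.05 to 0.15 below the model's prediction. The arm means are then overstated by 0.049 × 0.05 = 0.0025 to 0.049 × 0.15 = 0.007, and by 0.056 × 0.05 = 0.003 to 0.056 × 0.15 = 0.008. These nearly cancel. Placebo is not open-label SoC, so this does not show that bias is absent; it shows that its direction is not established.

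**Conclusion.** The conflict is real in the current text. Under footnote l, patients who stop may contribute no EQ-5D at later scheduled visits, and the later MMRM contrasts then rest on missing at random with no planned check. An early EOT interview before Week 24 falls in a Table 4 gap on 59% of days from Day 15 to Day 168. That share matters only if the interview is held early.

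The size and direction of any between-arm bias cannot be determined: the documents give no expected stopping rate for this trial, no EQ-5D standard deviation and no expected course after stopping.

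Severity is minor. EQ-5D is in no study objective, is listed under other endpoints in protocol Section 9.3, is treated as exploratory in Section 11.4.4, and lies outside the testing hierarchy. The primary and key secondary results are unaffected.

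**What to change.** Reconcile the three passages on the rule already in Section 10:

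- **Footnote l:** EQ-5D is collected in all randomized patients at Weeks 0, 4, 12, 24 and 36, whether or not they are still on study treatment, and additionally at any early EOT visit.
- **Section 10.3.4, first bullet:** name EQ-5D alongside the laboratory tests for which patients keep the visit schedule.

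This concerns data collection only and leaves the rules for stopping treatment as they are. The cost is two wording changes and a short questionnaire at visits these patients are already asked to attend.

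The change does not close the Table 4 gaps, but the scheduled visits that follow would supply in-window values, so an early value in a gap matters less. A sentence in SAP Section 2.4.7 on how such a value is used would be a useful addition.
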